QLQ-C30	Quality-of-life Questionnaire Core 30
QLQ-LC13	Quality-of-life Questionnaire Lung Cancer 13
RCT	Randomised controlled trial
REC	Research ethics committee
SAE	Serious adverse event
SAP	Statistical analysis plan
SD	Standard deviation
TIA	Transient ischemic attack
TNM	Classification of malignant tumours (TNM)
VAS	Visual analogue scale
VATS	Video assisted thorascopic surgery

1. INTRODUCTION TO SAP

1.1 Scope

This statistical analysis plan (SAP) details information regarding the statistical analysis of the VIOLET randomised controlled trial (RCT) and covers all analyses of study data outlined in the study protocol, with the exception of the health economic evaluation.

1.2 Editorial changes

Any changes made to this SAP after approval must be clearly justified and documented as an amendment at the end of this document. The SAP should then be re-approved.

1.3 SAP document approval

The co-director of the Clinical Trials and Evaluation Unit (CTEU) should authorise this document.

1.4 Skeleton tables and figures

Throughout this document references are made to any skeleton tables and figures to be used in the reporting of the study (e.g. **Figure F1** or **Table T1**). Such tables and figures can be found in **Appendix A** of this document and are intended as a guide for study reporting. Final versions of the tables/figures may differ: tables may be combined, and/or their layout or numbering may differ. However, the content should be consistent with **Appendix A**.

2. STUDY BACKGROUND AND OBJECTIVES

2.1 Study background

The VIOLET study is a multi-centre double-blind parallel RCT. It aims to test the superiority of video assisted thorascopic surgery (VATS) lobectomy versus open lobectomy in adult patients with early stage lung cancer.

2.2 Study objectives

The VIOLET study aims to compare the effectiveness, cost-effectiveness and acceptability of VATS lobectomy versus open surgery for treatment of lung cancer.

Specific objectives are to estimate:

- (a) The difference between groups in self-reported physical function at five weeks
- (b) The difference between groups with respect to a range of secondary outcomes including assessment of efficacy (hospital stay, pain, proportion and time to uptake of chemotherapy), measures of safety (adverse health events), oncological outcomes (proportion of patients upstaged to pN2 disease and disease-free survival) and overall survival.
- (c) The cost effectiveness of VATS and open surgery.

2.3 Primary outcome

The primary outcome is self-reported physical function, assessed using the QLQ-C30 questionnaire, at 5 weeks post-randomisation.

2.4 Secondary outcomes

Secondary outcomes are listed in the study protocol as:

- (1) Time from surgery to hospital discharge
- (2) Pain scores in the first two days post-surgery
- (3) Adverse health events to one year
- (4) Proportion and time to uptake of adjuvant treatment
- (5) Proportion of patients upstaged to pN2 disease
- (6) Overall and disease-free survival to one year
- (7) Proportion of patients who undergo complete resection (i.e. R(0) resection) during the procedure
- (8) Proportion of patients who experience prolonged incision pain (defined as the need of analgesia > 5 weeks post randomisation that was not being taken pre-operatively)
- (9) Generic and disease-specific HRQoL: EORTC QLQ-C30, QLQ-LC13 and EQ5D to one-year (measured at 2 weeks, 5 weeks, 3 months, 6 months and 12 months post-randomisation)
- (10) Resource use to one year (measured for the duration of post-operative hospital stay until discharge, and at 5 weeks, 3 months, 6 months and 12 months post-randomisation)

Additional secondary outcomes:

- (11) Proportion of patients upstaged to pN1 disease

As stated in section 1.1, outcome (10) is not covered in this SAP. Outcome (11) is not specified in the protocol but was added at the request of the chief investigator before any knowledge of the accruing data.

2.5 Changes to the study objectives during the course of the study

There have been several changes to the protocol since Research Ethics Committee (REC) approval was granted and the first centre opened to recruitment. These changes are summarised below.

October 2015	Removal of reference to RECIST criteria for disease assessment Addition of PIC sites
June 2017	Amended inclusion criteria to reflect inclusion of patients undergoing bi-lobectomy and the transition to TNM8 Clarification that events planned before surgery are not unexpected Details of phase 2 sites added
February 2018	Clarified location of 'bleeding' that is classified as an expected adverse event
January 2019	CTCAE grade changed to v5.0

The impact of these changes for the analysis of the study data are as follows:

- Transition to TNM8 – all patients staged under TNM7 will be restaged under TNM8
- Changes to eligibility criteria – eligibility will be assessed according to the protocol in place at the time of recruitment
- Changes to CTCAE grading – adverse events will be graded according to the CTCAE version in place at the time of the event

3. STUDY POPULATION

The study population is all patients aged ≥ 16 years of age who have been referred by the multi-disciplinary team (MDT) for lung resection for known or suspected lung cancer. Eligibility criteria are as inclusive as possible to promote the applicability of the evidence obtained during the trial. For specific inclusion/exclusion criteria see **Figure F1**.

Recruitment over time against targets will be presented overall (**Figure F2**).

The planned sample size for the VIOLET study is 498 patients. This sample size would be sufficient to detect a difference of 0.25 standard deviations in physical function between the VATS and open groups with 90% power and 5% significance (2-tailed). The total sample size will allow for a 20% dropout at one year.

3.1 Flow of participants

Participant flow will be described via a flowchart (see **Figure F1**). Follow-up will last 12 months with follow-up visits planned at 5 weeks, 3 months, 6 months and 12 months post-randomisation.

3.2 Randomisation

Patients are randomised (1:1 ratio) to either VATS lobectomy or open lobectomy. Randomisation will be stratified by study centre and minimised by surgeon. Randomisation will take place within one week of the planned operation date, once eligibility has been confirmed and consent given. The randomisation will take place using a secure password protected internet-based system.

3.3 Protocol deviations

The following types of protocol deviation will be considered:

- Patient did not meet the study eligibility criteria but was treated in the study.
- Patient did not undergo lobectomy
- Patient received the alternative intervention to that they were allocated (only includes patients who underwent a lobectomy)

Note it may be possible for patients to be classified as a protocol deviation for more than one reason.

The frequency of each type of deviation will be tabulated by treatment allocation (see **Table T1**).

3.4 Withdrawals

A patient (or a clinician on their behalf) can withdraw from the study at any time. In some cases, patients may be happy for data collection to continue, and therefore such patients will be included in the study analyses on an intention to treat basis (ITT), see **section 3.5**.

Data on all withdrawals is captured on a specific case report form (CRF) and will be tabulated by treatment allocation; see **Table T2**.

3.5 Analysis population

The analysis population consists of all randomised patients excluding:

- Patients who died after randomisation but prior to any data collection.

- Patients withdrawn who were unwilling for data collected to be used.

The main study analyses will be performed on an ITT basis, including randomised participants who are not found to have lung cancer. A modified ITT analysis excluding these participants will also be performed for the primary outcome.

3.6 Safety population

The safety population for the main trial analyses will consist of **all** randomised patients, excluding patients withdrawn who were unwilling for data collected to be used.

Participants will be grouped according to the treatment allocated and events in participants who received the alternative treatment (e.g. VATS received by participant randomised to open or vice versa), did not undergo a lobectomy, or received no treatment will be detailed in footnotes.

4. DATA COLLECTION

A summary of data collection is shown below.

Measurement	Pre-randomisation	Day of surgery	1-day post-surgery	2 days post-surgery	Discharge	Post-randomisation				
	Baseline					2 weeks	5 weeks	3 months	6 months	1 year
Eligibility	X									
Imaging review (CT / PET-CT)	X									
Participant characteristics	X									
Audio recorded consultation	X									
Lobectomy via VATS or Open Surgery		X								
Intra-operative details		X								
Histopathology staging		X								
Tumour sample for research		X								
Patient questionnaires										
QLQ-C30	X					X	X	X	X	X
QLQ-LC13	X					X	X	X	X	X
EQ5D	X					X	X	X	X	X
Bang Blinding Index				X	X					
Pain score	X		X	X						
Adverse Events				X			X	X	X	X
Resource use	X			X			X	X	X	X
CT scan of chest & abdomen										X

5. DERIVATIONS

5.1 Primary outcome

The primary outcome is self-reported physical function (QLQ-C30) at 5 weeks post randomisation. Physical function will be measured at baseline, 2 weeks, 5 weeks, 3, 6 and 12 months.

New variable	Rules
Physical functioning (PF2) raw score	At each time point: = mean of questions 1 to 5, if at least three of the questions are non-missing MISSING: otherwise
PF2 overall score	At each time point: = $[1 - (\text{PF2 raw score} - 1) / 3] * 100$

5.2 Secondary outcomes

1. Time from surgery to hospital discharge

Both time from surgery until first fit for discharge, and time from surgery until hospital discharge will be described. Time from surgery until hospital discharge will be compared between groups.

New variable	Rules
Time from surgery to hospital discharge	= (Discharge date – operation date)
Fit for discharge	YES: if satisfactory mobility = YES AND pain under control with oral analgesia = YES AND satisfactory Hb & electrolytes = YES AND satisfactory chest X-ray = YES (or satisfactory on a previous day and not necessary to repeat) AND free from complications requiring treatment = YES NO: if satisfactory mobility = NO OR pain under control with oral analgesia = NO OR satisfactory Hb & electrolytes = NO OR satisfactory chest X-ray = NO (or not done and not previously satisfactory) OR free from complications requiring treatment = NO MISSING: otherwise
Time from surgery to fit for discharge	= (First day fit for discharge – operation date)

2. Pain scores in the first two days post-surgery

Pain scores are collected at baseline (prior to surgery), day one post-surgery and day two post-surgery. Pain scores are collected directly on CRFs using the visual analogue scale (VAS) and so no derivation is required.

3. Adverse health events to 1 year

All adverse events occurring at any time during the 12 month follow-up period will be reported.

New variable	Rules
Maximum intensity of SAE (CTCAE)	Maximum of CTCAE variable on initial SAE form and all follow-up SAE forms

4. Proportion and time to uptake of adjuvant treatment

The proportion of patients receiving adjuvant treatment at any time during the 12 month follow-up period will be described. The time to uptake of adjuvant treatment will be calculated as follows:

New variable	Rules
Uptake of adjuvant treatment	YES: if at any study visit, chemotherapy or radiotherapy started = YES NO: if at all attended study visits, chemotherapy and radiotherapy started = NO MISSING: otherwise
Time to uptake of adjuvant therapy	= (Earliest chemotherapy/radiotherapy start date - randomisation date)

5. Proportion of patients upstaged to pN2 disease after the procedure

The proportion of patients upstaged to pathological N2 disease following surgery will be derived as follows:

New variable	Rules
Upstaged to pN2	YES: if pathological disease stage of primary tumour = N2 NO: if pathological disease stage of primary tumour = N0 OR N1 NOT CANCER: no cancer, sample benign MISSING: otherwise

6. Overall and disease-free survival to 1 year

Both overall and disease-free survival to 12 months will be compared between groups.

New variable	Rules
Time to death (days)	(Death date – randomisation date)
Death censor variable	YES: if patient did not die before the end of follow-up NO: if patient died before the end of follow-up MISSING: otherwise
Time to disease progression (days)	(Date of earliest disease recurrence – randomisation date)
Disease progression censor variable	YES: if patient did not have disease progression before the end of follow-up NO: if patient had disease progression before the end of follow-up MISSING: otherwise

7. Proportion of patients who undergo complete resection during the procedure

Completeness of the resection will be defined as follows:

New variable	Rules
Complete resection	YES: if resection completeness = R0 (no residual tumour) NO: if resection completeness = R1 (microscopic residual tumour) OR R1 (other than microscopic residual tumour) OR R2 (macroscopic residual tumour) MISSING: otherwise

8. Proportion of patients who experience prolonged incision pain

Prolonged incision pain is defined as the need for analgesia after 5 weeks post-randomisation.

New variable	Rules
Prolonged incision pain	YES: if patient continuously prescribed analgesia until after 5 weeks post-randomisation that was not being taken preoperatively NO: if patient not continuously prescribed analgesia until after 5 weeks post-randomisation OR patient continuously prescribed analgesia that was administered pre-operatively until after 5 weeks MISSING: otherwise

9. General and disease-specific HRQoL: EORTC QLQ-C30, QLQ-LC13 and EQ5D to 1 year

The QLQ-C30, QLQ-LC13 and EQ5D questionnaires are completed at baseline, 2 weeks, 5 weeks, 3, 6 and 12 months. Details for how to derive the overall and sub-scale scores for these three questionnaires can be found below in the respective tables. The EORTC core questionnaire and associated modules scoring manual will be used to derive the QLQ-C30 and QLQ-LC13 scores ⁽¹⁾.

New variable – QLQ-C30	Rules
Global health status (QL2) raw score	At each time point: = mean of question 29 and 30, if both non-missing MISSING: otherwise
QL2 overall score	At each time point: = $[(\text{QL2 raw score}-1)/6] * 100$
Role functioning (RF2) raw score	At each time point: = mean of question 6 and 7, if both non-missing MISSING: otherwise
RF2 overall score	At each time point: = $[1 - (\text{RF2 raw score}-1)/3] * 100$
Emotional functioning (EF) raw score	At each time point: = mean of questions 21 to 24, if at least two questions are non-missing MISSING: otherwise
EF overall score	At each time point: = $[1 - (\text{EF raw score}-1)/3] * 100$

Cognitive functioning (CF) raw score	At each time point: = mean of question 20 and 25, if both non-missing MISSING: otherwise
CF overall score	At each time point: = $[1 - (\text{CF raw score} - 1) / 3] * 100$
Social functioning (SF) raw score	At each time point: = mean of question 26 and 27, if both non-missing MISSING: otherwise
SF overall score	At each time point: = $[1 - (\text{SF raw score} - 1) / 3] * 100$
Fatigue (FA) raw score	At each time point: = mean of questions 10, 12 and 18, if at least two are non-missing MISSING: otherwise
FA overall score	At each time point: = $[(\text{FA raw score} - 1) / 3] * 100$
Nausea and vomiting (NV) raw score	At each time point: = mean of questions 14 and 15, if both non-missing MISSING: otherwise
NV overall score	At each time point: = $[(\text{NV raw score} - 1) / 3] * 100$
Pain (PA) raw score	At each time point: = mean of questions 9 and 19, if both non-missing MISSING: otherwise
PA overall score	At each time point: = $[(\text{PA raw score} - 1) / 3] * 100$
Dyspnoea (DY) raw score	At each time point: = question 8 MISSING: otherwise
DY overall score	At each time point: = $[(\text{DY raw score} - 1) / 3] * 100$
Insomnia (SL) raw score	At each time point: = question 11 MISSING: otherwise
SL overall score	At each time point: = $[(\text{SL raw score} - 1) / 3] * 100$
Appetite loss (AP) raw score	At each time point: = question 13 MISSING: otherwise
AP overall score	At each time point: = $[(\text{AP raw score} - 1) / 3] * 100$
Constipation (CO) raw score	At each time point: = question 16 MISSING: otherwise
CO overall score	At each time point: = $[(\text{CO raw score} - 1) / 3] * 100$
Diarrhoea (DI) raw score	At each time point: = question 17 MISSING: otherwise
DI overall score	At each time point: = $[(\text{DI raw score} - 1) / 3] * 100$
Financial difficulties (FI) raw score	At each time point: = question 28 MISSING: otherwise
FI overall score	At each time point: = $[(\text{FI raw score} - 1) / 3] * 100$

New variable – QLQ-LC13	Rules
Dyspnoea (LCDY) raw score	At each time point: = mean of questions 3 to 5, if all three questions are non-missing MISSING: otherwise
LCDY overall score	At each time point: = $[(LCDY \text{ raw score}-1)/3] * 100$
Coughing (LCCO) raw score	At each time point: = question 1 MISSING: otherwise
LCCO overall score	At each time point: = $[(LCCO \text{ raw score}-1)/3] * 100$
Haemoptysis (LCHA) raw score	At each time point: = question 2 MISSING: otherwise
LCHA overall score	At each time point: = $[(LCHA \text{ raw score}-1)/3] * 100$
Sore mouth (LCSM) raw score	At each time point: = question 6 MISSING: otherwise
LCSM overall score	At each time point: = $[(LCSM \text{ raw score}-1)/3] * 100$
Dysphagia (LCDS) raw score	At each time point: = question 7 MISSING: otherwise
LCDS overall score	At each time point: = $[(LCDS \text{ raw score}-1)/3] * 100$
Peripheral neuropathy (LCPN) raw score	At each time point: = question 8 MISSING: otherwise
LCPN overall score	At each time point: = $[(LCPN \text{ raw score}-1)/3] * 100$
Alopecia (LCHR) raw score	At each time point: = question 9 MISSING: otherwise
LCHR overall score	At each time point: = $[(LCHR \text{ raw score}-1)/3] * 100$
Pain in chest (LCPC) raw score	At each time point: = question 10 MISSING: otherwise
LCPC overall score	At each time point: = $[(LCPC \text{ raw score}-1)/3] * 100$
Pain in arm or shoulder (LCPA) raw score	At each time point: = question 11 MISSING: otherwise
LCPA overall score	At each time point: = $[(LCPA \text{ raw score}-1)/3] * 100$
Pain in other parts (LCPO) raw score	At each time point: = question 12 MISSING: otherwise
LCPO overall score	At each time point: = $[(LCPO \text{ raw score}-1)/3] * 100$

Pain medication (LCPM) raw score	At each time point: = question 13 MISSING: otherwise
LCPM overall score	At each time point: = [(LCPM raw score-1)/3] * 100

New variable – EQ5D	Rules
EQ5D single summary index score	Five digit 'state' score is derived as: 10000*mobility score + 1000*self-care score + 100*usual activities score + 10*pain/discomfort score + anxiety/depression score. Each state score is then assigned a single summary index score according to reference scales. These index scores are numerical and range from -0.59 to 1.00, with a score of 1.00 denoting perfect health.

10. Proportion of patients upstaged to pN1 disease after the procedure

The proportion of patients upstaged to pathological N1 disease following surgery will be derived as follows:

New variable	Rules
Upstaged to pN1	YES: if clinical disease stage of primary tumour = N0 AND pathological disease stage of primary tumour = N1 NO: if either: 
 pathological disease stage of primary tumour = N0 OR N2 clinical disease stage of primary tumour = N1 NOT CANCER: no cancer, sample benign MISSING: otherwise

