6.2.2 Analysis models

All outcomes listed in the study protocol will be presented as per the template tables **Table T11 to T18**. General methods of presentation and assessing treatment effects are outlined below. For all treatment comparisons, the open lobectomy group will be the reference group. Details specific to each outcome are described as appropriate.

Each outcome will be considered under a certain data type, as outlined in the table below:

Date type	Outcomes
Binary	Proportion of patients receiving adjuvant treatment Proportion of patients who undergo complete resection during the procedure Proportion of patients who experience prolonged incision pain Any in-hospital adverse event Any in-hospital serious adverse event
Categorical	Proportion upstaged to pN1 disease after the procedure Proportion upstaged to pN2 disease after the procedure
Time to event	Time from surgery to hospital discharge Time to uptake of adjuvant treatment Overall survival Disease-free survival
Longitudinal	Physical function (primary) Pain scores in the first two days post-surgery HRQoL (QLQ-C30, QLQ-LC13, EQ5D)

Each type of data will be summarised and compared between the groups according to the following:

- **Binary outcomes** will be presented as numbers and percentages of patients in each treatment group. Outcomes will be compared between treatment groups using generalised linear models, with treatment comparison estimates presented as adjusted risk ratios (RR) and risk differences (RD) with 95% confidence intervals (95% CI). Formal statistical comparisons of treatment effects will only be performed if more than ten patients in total experience the outcome (with at least one event in each treatment group).
- **Categorical outcomes** will be presented as numbers and percentages of patients in each treatment group in each category. Outcomes will be compared between treatment groups using multinomial logistic regression, with treatment comparison estimates presented as adjusted RR and 95% CI.

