- **Time to event outcomes** will be summarised by the median and IQR or mean and SD in each treatment group, estimated from survival modelling. Outcomes will be compared using Cox’s proportional hazards, parametric models, or interval censoring methods for analysing discrete time data, as appropriate. The choice of model used will depend on the outcome event and the distribution of the data. Treatment comparisons will be presented as hazard ratios (HRs) and 95% CI if a proportional hazards model is used, time ratios (TRs) and 95% CI if an accelerated failure time model is used, or OR and 95% CI if a discrete time proportional odds model is used. Times will be censored using censoring variables defined below:

Outcome	Censor variable
Time from surgery to hospital discharge	Date of death, if patient died before hospital discharge
Time to uptake of adjuvant treatment	Last visit date, if patient did not receive any adjuvant treatment
Overall survival	Last visit date, if patient was alive at the end of the study follow-up
Disease free survival	Last visit date, if patient was disease free at the end of the study follow-up

- **Continuous longitudinal outcomes** will be summarised as means and SDs (or medians and IQRs if distributions are skewed) at each time point. Outcomes will be compared using linear mixed effects methodology with the treatment group and study design variables fitted as per section 5.2.1, and patient terms fitted as random effects. Separate parameter estimates will be incorporated into models for 1) the mean baseline response across both treatment groups and 2) at each post-intervention time point for each treatment (i.e. saturated model with time fitted as a categorical variable). If the time x treatment interaction (post-intervention) is not statistically significant at the 10% level an overall treatment effect will be reported. If the interaction is statistically significant the changes in treatment effect with time will be described. Deaths will be accounted for by modelling HRQoL and survival jointly. When modelling EQ5D, patients who have died will be assigned a score of 0 for all future time points. Different variance/covariance structures will be explored, and the structure that provides the best fit in terms of information criteria such as AIC, BIC and likelihood ratio tests will be used. Treatment comparisons will be presented as adjusted differences in means with 95% CI.

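### Adjuvant uptake is derived without regard to recurrence, so treatment for relapse can be scored as uptake; separately, the binary proportion codes living patients lost early as definite non-uptake

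*SAP*

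**What the plan says.** Section 2.2(b) places the outcome among the efficacy measures: "assessment of efficacy (hospital stay, pain, proportion and time to uptake of chemotherapy". Section 2.4 lists it as uptake of adjuvant treatment, and Section 5.2, item 4, derives it from chemotherapy and radiotherapy together:

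- Window: "The proportion of patients receiving adjuvant treatment at any time during the 12 month follow-up period will be described".
- Uptake present: "YES: if at any study visit, chemotherapy or radiotherapy started = YES".
- Uptake absent: "NO: if at all attended study visits, chemotherapy and radiotherapy started = NO". Anything else is missing.
- Time to uptake: "Earliest chemotherapy/radiotherapy start date - randomisation date".

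Section 6.2.2 analyses "Proportion of patients receiving adjuvant treatment" as a binary outcome, by risk ratio and risk difference, and time to uptake as a time-to-event outcome. The censoring rule for the latter is "Last visit date, if patient did not receive any adjuvant treatment". Table T13 gives both outcomes an effect estimate and a p-value.

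Section 5.2, item 6, derives the date of first recurrence for disease-free survival to one year. The uptake rules do not use that date.

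**The concern.** Adjuvant treatment follows surgery and precedes any relapse. The derivation asks only whether chemotherapy or radiotherapy was started. Take a patient who has no adjuvant treatment, relapses at month 7 and then starts radiotherapy. Read literally, the rule records uptake at month 7. The SAP expects relapses within the same 12 months, since it analyses disease-free survival over that period. If recurrence differs between arms, recorded uptake differs too, even when the true use of adjuvant treatment is identical.

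The second problem concerns only the binary proportion. The absent category looks at attended visits alone and sets no minimum follow-up. A patient seen at 5 weeks, untreated, and then lost alive is a definite NO. That patient never counts towards the 5% missing-data threshold in Section 6.2.8. For time to uptake, Section 6.2.2 censors the same patient at the last visit, so the two analyses treat one patient in two ways. Section 3 allows for 20% dropout at one year, so such patients are to be expected.

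**Working it through.** The SAP states no rate or power for this outcome, so there is no figure to reproduce. All rates below are assumptions. The planned 498 patients at 1:1 give 249 per arm.

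**1. Relapse treatment scored as uptake**

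Let p be true adjuvant uptake (equal in both arms), r the 12-month recurrence among patients without adjuvant treatment, and f the share of those relapses treated with chemotherapy or radiotherapy within the window.

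Recorded uptake = p + (1 − p) × r × f, so the false difference between arms is (1 − p) × f × (difference in r).

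With p = 0.20 and f = 0.5:

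| Recurrence, open v VATS | Recorded, open | Recorded, VATS | VATS − open | RR |
|---|---|---|---|---|
| 12% v 8% | 0.20 + 0.80 × 0.12 × 0.5 = 24.8% | 0.20 + 0.80 × 0.08 × 0.5 = 23.2% | −1.6 points | 0.94 |
| 15% v 8% | 0.20 + 0.80 × 0.15 × 0.5 = 26.0% | 23.2% | −2.8 points | 0.89 |

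Standard error in the first row: √[(0.248 × 0.752 + 0.232 × 0.768) / 249] = 3.8 points. The two false differences are about 0.4 and 0.7 standard errors.

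Over a wider range (p 15% to 35%, r 5% v 8% to 15%, f 50% to 80%), recorded uptake is higher in the arm with more relapses by 1.0 to 6.8 points (RR 1.03 to 1.37). A middle case (p = 25%, r = 5% v 10%, f = 80%) gives 28.0% v 31.0%, with about an 11% chance of p < 0.05. The extreme case (p = 15%, r = 5% v 15%, f = 80%) gives 18.4% v 25.2%, with about a 45% chance.

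The hazard ratio is affected through the same events. Its shift was not sized, because that would need assumed timings as well.

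**2. Early loss coded NO (binary proportion only)**

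Let l be the share lost alive after at least one visit but before treatment would have started. Recorded uptake = p × (1 − l). With p = 25%:

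- loss 5% v 10%: 23.75% v 22.5%, RR 0.95
- loss 5% v 20%: 23.75% v 20.0%, RR 0.84

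This lowers recorded uptake in the arm with more loss.

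**3. Both together**

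Take one arm with more of both: r = 5% v 10%, f = 80%, l = 5% v 10%. Multiply the result of step 1 by (1 − l). For p = 25%: 0.28 × 0.95 = 26.6% v 0.31 × 0.90 = 27.9%, a difference of +1.3 points, against +3.0 from relapse treatment alone. For p = 15% and 35% the net differences are +2.1 and +0.5 points. The two biases partly cancel here.

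**4. Would setting early losses to missing solve it?**

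Suppose true uptake is 25% in both arms, all started early, and later loss is 15% v 5%. The present rule gives 25% v 25%. If untreated patients lost later become missing, complete cases give 25 / (100 − 0.15 × 75) = 25 / 88.75 = 28.2% v 25 / (100 − 0.05 × 75) = 25 / 96.25 = 26.0%. Only untreated patients are removed, so this creates a difference where none exists.

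**The case against.** The best reply is that the rule stands under a heading about adjuvant treatment and reads a case report form field that is not shown. If that field records adjuvant treatment only, most of the first problem disappears. This stands as a condition on the finding. It does not remove the finding, because the SAP text states no such restriction.

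A second reply is that the effect is small. The only study CT scheduled after surgery is at one year (Section 4), and relapses first found then could rarely be treated inside the window, so f = 0.5 may be high. At f = 0.25 the two examples shrink to 0.80 × 0.25 × 0.04 = 0.8 and 0.80 × 0.25 × 0.07 = 1.4 points. Disease-free survival also stands beside uptake in Table T13, so a reader could see a recurrence difference. Both remarks are fair. They limit the weight of the point but do not justify leaving the rule open.

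Third, early loss is already handled in time to uptake by censoring, and a patient who died untreated did not receive adjuvant treatment. Both are correct, so the second problem covers only living patients lost early, and only the proportion.

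A reader might infer that both features flatter the arm with more relapses. The documents do not support that. Coding early losses as NO lowers uptake in the arm with more loss and can work against the first bias. The SAP also lists uptake under efficacy without saying that more or earlier uptake is favourable.

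**Conclusion.** The point holds in limited form. As written, the derivation counts any chemotherapy or radiotherapy started within 12 months, and both the proportion and the time to uptake inherit this. A difference in recurrence then shifts the risk ratio, risk difference and hazard ratio without any difference in adjuvant treatment. The shift in the proportion is 1.6 to 2.8 points under the main assumed rates and 1.0 to 6.8 points over the wider range. This rests on the form field not being restricted to adjuvant treatment and on recurrence differing between arms.

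Coding living, untreated patients lost early as NO is a distinct bias in the proportion alone, and its direction depends on which arm loses more patients. It would be too strong to say that the plan will mislead on this outcome: the outcome is secondary, the main examples lie within one standard error, and the two biases may offset. The rule is nevertheless formally tested and cheap to correct, so it should be corrected.

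**What to change.** - **Uptake.** Score YES only if the earliest post-operative chemotherapy or radiotherapy start date precedes the date of first recurrence, or the treatment is recorded as adjuvant. With no recurrence recorded, any post-operative start counts. If the form field already captures adjuvant treatment only, say so in Section 5.2.
- **Time to uptake.** Apply the same condition, and treat recurrence and death before uptake as competing events.
- **Proportion.** Report it as 12-month cumulative incidence with the same competing events, censoring living patients at their last visit. Do not set untreated patients lost early to missing, for the reason shown in step 4 of the working.
- **Benign disease.** These patients are followed only to 5 weeks by design (note to Figure F1 in Appendix A). Keep them as not having uptake through 12 months, so that they are neither missing nor censored at 5 weeks.

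The cost is a few lines of SAP text and derivation code. The treatment start and first recurrence dates are already used in Section 5.2. Recorded uptake will be slightly lower, and a few borderline dates, where treatment and recurrence fall close together, will need checking.
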